6.2.2. Baseline/Day 1 Assessments

The following evaluations are to be completed at the Day 1 visit. The investigator must have confirmed eligibility before proceeding with randomization on the Day 1 visit. If the screening and Day 1 visits occur within 24 hours, no procedures need to be repeated. Participants must complete the following assessments before being administered study drug:

- Physical examination including, vital signs (heart rate, temperature, blood pressure, and body weight)
- Documentation of respiratory status:

Respiratory rate

— Oxygen supplementation: room air, low flow O₂ (L/min and %), high flow O₂ (L/min and %), CPAP/BIPAP (FiO₂ or %), mechanical ventilation (FiO₂ or %), ECMO

Oxygenation: SpO₂ or PaO₂

Radiographic findings (if available)

- Review AEs and document concomitant medications
- Obtain blood samples for white blood cell count, hemoglobin and/or hematocrit, platelets, creatinine and creatinine clearance, glucose, total bilirubin, ALT, AST

- SARS-CoV-2 Testing: Collect nasopharyngeal swab sample for subjects/sites participating in this portion of the study
- Review Ordinal Scale (Section 6.9)

6.3. Daily Study Assessments (Days 2-14)

The following evaluations are to be completed daily from Days 2–14 or until discharge whichever comes earlier:

- Vital signs (heart rate, temperature, blood pressure), body weight (if available).
- A symptom-directed (targeted) physical examination will be performed to evaluate for any possible adverse event
- Documentation of respiratory status:

Respiratory Rate

— Oxygen supplementation: room air, low flow O₂ (L/min and %), high flow O₂ (L/min and %), CPAP/BIPAP (FiO₂ or %), mechanical ventilation (FiO₂ or %), ECMO

Oxygenation: SpO₂ or PaO₂

Radiographic findings (if available)

- SARS-CoV-2 testing results if available should be reported
- Review AEs and document concomitant medications
- Review Ordinal Scale (Section 6.9)

6.4. Additional Assessments

The following evaluations are to be completed at the following visits or until discharge, whichever comes earlier:

- Safety laboratory tests (white blood cell count, hemoglobin and/or hematocrit, platelets, creatinine and creatinine clearance, glucose, total bilirubin, ALT, AST) are to be completed at Days 3, 5, 8, 10, and 14

█

[REDACTED]

- SARS-CoV-2 Testing: Collect nasopharyngeal swab sample at Days 3, 5, 8, 10, and 14 for subjects/sites participating in this portion of the study

6.5. Day 28 Follow up Assessment (\pm 5 Days)

The following evaluations are to be completed if this visit is conducted in person. For participants who have been discharged from hospital, the final evaluation can be made by phone. Only AE and concomitant medication and ordinal scale (if discharged on or after Day 14) review are to be completed if visit is conducted by phone.

- Physical examination and vital signs (heart rate, temperature, blood pressure)
- Documentation of respiratory status:

Respiratory rate

— Oxygen supplementation: room air, low flow O₂ (L/min and %), high flow O₂ (L/min and %), CPAP/BIPAP (FiO₂ or %), mechanical ventilation (FiO₂ or %), ECMO

Oxygenation: SpO₂ or PaO₂

Radiographic findings (if available)

- Review AEs and document concomitant medications
- Review the Ordinal Scale (Section 6.9). If subject was not discharged by Day 14, any change in category and the date of any change in category from Day 14 to discharge (or Day 28) should be recorded

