8.9. Sample Size

The sample size computation is based on an assumed distribution of the 7-point ordinal scale on Day 11 for the SOC treatment group. The odds ratio represents the odds of improvement in the 7-point ordinal scale for an RDV treatment group relative to the SOC treatment group. The sample size needed to detect a given odds ratio for a 1:1 randomization using a 2-tailed test at level α is given by:

$$12 (z_{\alpha/2} + z_{\beta})^2 / \theta^2 (1 - \sum_{i=1}^7 \rho_i^3)$$

Where θ is the log odds ratio, ρ_i is the overall probability (combined over both treatment groups) of being in the i th category of the ordinal outcome, and $z_{\alpha/2}$ and z_{β} are the $1 - \alpha/2$ and β quantiles of the standard normal distribution {Whitehead 1993}.

A sample size of 600 participants (200 in each group) achieves > 85% power to detect an odds ratio of 1.8 using a two-sided significance level of 0.05 for comparing each RDV group (n = 200) to standard of care group (n = 200). In this sample size calculation, it is assumed that the probability distribution of the ordinal scale at Day 11 for Treatment Group 3 is as follows:

1. Death, 0.5%
2. Hospitalized, on invasive mechanical ventilation or ECMO, 2.5%
3. Hospitalized, on non-invasive ventilation or high flow oxygen devices, 7%
4. Hospitalized, requiring low flow supplemental oxygen, 8%
5. Hospitalized, not requiring supplemental oxygen - requiring ongoing medical care (COVID-19 related or otherwise), 15%
6. Hospitalized, not requiring supplemental oxygen - no longer requires ongoing medical care (other than per protocol RDV administration), 27%
7. Not hospitalized, 40%

The sample size calculation was done using software PASS (Version 14.0).

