Appendix 2. Study Procedures Table

	Screening	Baseline / Day 1 ^b	Day 2	Day 3	Day 4	Day 5	Days 6 and 7	Day 8	Day 9	Day 10	Days 11, 12 and 13	Day 14	Day 28 ^c Follow-up (± 5 days)
Written Informed Consent	X												
Medical History	X												
Physical Examination	X	X	X	X	X	X	X	X	X	X	X	X	X
Height	X												
Vital Signs ^d	X	X	X	X	X	X	X	X	X	X	X	X	X
Study Laboratory Testing	X	X		X		X		X		X		X	
Respiratory Status	X	X	X	X	X	X	X	X	X	X	X	X	X
Ordinal Scale		X	X	X	X	X	X	X	X	X	X	X	X
Pregnancy Test	X												
CCI													
Virologic Testing ^e		X		X		X		X		X		X	
RDV Dosing for Group 1		X	X	X	X	X							
RDV Dosing for Group 2		X	X	X	X	X	X	X	X	X			
Adverse Events	X	X	X	X	X	X	X	X	X	X	X	X	X
Concomitant Medications	X	X	X	X	X	X	X	X	X	X	X	X	X

- a Includes heart rate, respiratory rate, temperature, blood pressure, SpO₂, and body weight. Body weight collected on Screening and Day 1 and otherwise if available.
- b Assessments need not be repeated if performed within 24 hours of screening procedures; data collection other than adverse events and concomitant medications should stop at Day 14 or discharge, whichever is earlier.
- c Day 28 evaluations completed if the visit is conducted in person. Only adverse event and concomitant medications review completed if visit conducted by phone.
- d [REDACTED]
- e Virologic (SARS CoV 2) testing for subjects/sites participating in this portion of the study on Days 1, 3, 5, 8, 10, and 14.

Appendix 3. Pregnancy Precautions, Definition for Female of Childbearing Potential, and Contraceptive Requirements

1) Definitions

a. Definition of Childbearing Potential

For the purposes of this study, a female born subject is considered of childbearing potential following the initiation of puberty (Tanner stage 2) until becoming post-menopausal, unless permanently sterile or with medically documented ovarian failure. No documentation of Tanner stage will be required for people unless deemed prepubescent.

Women are considered to be in a postmenopausal state when they are ≥ 54 years of age with cessation of previously occurring menses for ≥ 12 months without an alternative cause. In addition, women of any age with amenorrhea of ≥ 12 months may also be considered postmenopausal if their follicle stimulating hormone (FSH) level is in the postmenopausal range and they are not using hormonal contraception or hormonal replacement therapy.

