6.2. Efficacy Endpoints of Interest

Efficacy endpoints of interest include endpoints based on clinical status assessed by a 7-point ordinal scale. The endpoint will be derived by combining the available death, hospital discharge alive and ordinal scale assessment reported by the site, where death supersedes discharge alive and discharge alive supersedes the ordinal scale score reported by the site. The proportion of participants for each ordinal scale category is expressed as percentages for presentation purpose.

Sites were instructed to report the worst ordinal scale category for each day. Therefore, the ordinal scale result on the day the participant was discharged alive does not necessarily reflect Not hospitalized (7). The definition of clinical status based on the 7-point ordinal scale is defined as follows:

- If a participant dies while hospitalized (as recorded on the Death eCRF and Hospitalization eCRF), the endpoint on the day of death and all subsequent days through Day 28 will be set to Death (1)
- If the participant is discharged alive, the endpoint on the day of discharge alive and all subsequent days through Day 28 will be set to Not hospitalized (7)
- If the participant is discharged alive and dies on the same day or a later day (as recorded on the Death eCRF and Hospitalization eCRF), the endpoint on the day of discharge alive and all subsequent days until the day of death will be set to Not hospitalized (7). On the day of death and all subsequent days through Day 28, the endpoint will be set to Death (1),

Every effort will be made to obtain clinical status data for all participants prior to discharge alive. The last known clinical status will be used for days with missing clinical status (eg, where the reason for Hospital Discharge is not "Discharged Alive" and the participant has not died). All post-baseline days with missing ordinal scale score, from Day 2 to Day 14 and Day 28, will use the previous last known clinical status.

Efficacy endpoints of interest include

- Clinical status on Days 1 to 14, Day 28 and last available assessment
- Change in clinical status on Days 5, 7, 11, 14, 28, and last available assessment
- Time to clinical improvement (days): Clinical improvement is defined as a ≥ 2-point improvement from baseline clinical status or discharged alive on the 7-point ordinal scale using the definition specified above.

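### Protocol 6.5 and Appendix 2 disagree on whether the Day 28 phone contact asks clinical status, and for a small group the Part B SAP assumes a status that could have been asked

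*Protocol*

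**What the plan says.** **Collection.** Protocol 6.5 allows a remote final contact: "For participants who have been discharged from hospital, the final evaluation can be made by phone". For that contact, "Only AE and concomitant medication and ordinal scale (if discharged on or after Day 14) review are to be completed". The in-person list in the same section includes the ordinal scale with no limit on discharge date. For participants still in hospital at Day 14, "any change in category and the date of any change in category from Day 14 to discharge (or Day 28) should be recorded".

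Protocol Appendix 2 marks the ordinal scale in the Day 28 column, but footnote c reads: "Only adverse event and concomitant medications review completed if visit conducted by phone". SAP Appendix 1 repeats this. Both tables also say that data other than adverse events and concomitant medications stop being collected at Day 14 or discharge, whichever comes first (footnote b in the protocol's table).

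**Analysis (Part B).** SAP 6.2 ranks its sources: "death supersedes discharge alive and discharge alive supersedes the ordinal scale score reported by the site". For a live discharge, "the endpoint on the day of discharge alive and all subsequent days through Day 28 will be set to Not hospitalized (7"), with death as the only stated exception. For the rest, "The last known clinical status will be used for days with missing clinical status". The SAP's own example is a participant who has not died and whose discharge reason is other than Discharged Alive. The carry-forward covers Days 2 to 14 and Day 28.

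**The concern.** A Day 28 contact is planned for everyone, yet whether clinical status is recorded depends on how the contact is made, on the day of discharge, and on which of two conflicting instructions the site follows. Where nothing is recorded, the SAP supplies a value.

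That matters for two kinds of participant. One left hospital before Day 14 for a reason other than a live discharge, a transfer being one possibility. This person may since have recovered or worsened but keeps an in-hospital score. The other was discharged alive, is in hospital again on Day 28 for a reason unrelated to COVID-19, and is still scored 7. By the wording of the scale (Protocol 6.9) this second person belongs below 7, because category 5 covers inpatient care whether or not it is related to COVID-19.

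At stake are the Part B Day 28 summaries: category, change from baseline, percentage improved or recovered, and shift in oxygen support.

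**Working it through.** **1. The rules side by side.**

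| Participant | Asked by phone, 6.5 | Asked by phone, footnote c | Asked in person, 6.5 | Day 28 value, SAP 6.2 |
|---|---|---|---|---|
| Discharged alive before Day 14 | no | no | yes | 7 unless dead, whatever is reported |
| Discharged alive, Day 14 or later | yes | no | yes | 7 unless dead, whatever is reported |
| Left before Day 14, other reason | no | no | yes | last known status if nothing is reported |
| Left Day 14 or later, other reason | yes | no | yes | reported status if any, otherwise last known |

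The second and third columns disagree in rows 2 and 4. The phone limit in 6.5 can change an analysed value only in row 3. In rows 1 and 2 the SAP hierarchy fixes the value at 7, so asking the question changes nothing unless the SAP changes too.

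**2. The plan's own figure.** Protocol 8.9 states more than 85% power for 200 versus 200 at an odds ratio of 1.8, two-sided 0.05. The printed formula gives N = 12(z + z)² / [θ²(1 − Σp³)], with N the total of two groups.
- θ = ln 1.8 = 0.588, so θ² = 0.3455.
- Averaging the SOC distribution with the same distribution shifted by 1.8 gives Σp³ = 0.125, so 1 − Σp³ = 0.875.
- At N = 400: √(400 × 0.3455 × 0.875 / 12) = 3.17. Subtracting 1.96 leaves 1.21, which is 88.8% power.

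The stated figure is reproduced. It concerns Day 11, so nothing here alters it.

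**3. How many would not be asked by phone.** The documents give no share discharged before Day 14. The nearest input is the SOC planning assumption for Day 11, "Not hospitalized, 40" per cent.
- RDV at the design effect: odds 0.40/0.60 × 1.8 = 1.2, and 1.2/2.2 = 54.5%.
- Part B, all RDV: about 545 of 1000, or 400 of 1000 with no drug effect (40%).
- Part A: (40 + 2 × 54.5)/3 = 49.7%, about 298 of 600.
- Day 11 is a floor for before Day 14. If everyone in category 6 also left by Day 13 (an assumption), the Part B share is 67% with no effect. At odds ratio 1.8 it is 0.67/0.33 × 1.8 = 3.65, and 3.65/4.65 = 78.5%.

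These shares count people not asked if all were followed by phone. They do not count wrong values.

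**4. How many values could be wrong.**
- *Carried-forward scores.* The frequency of other discharge reasons is not given. Assuming 1% to 3% of 1000 gives 10 to 30. This is an upper figure, because it is not yet restricted to those who left before Day 14 and were followed by phone. If every one were misclassified in the same direction, a Day 28 percentage would move by 10/1000 to 30/1000, or 1 to 3 points. Someone who left on Day 13 at the latest has a score carried for at least 28 − 13 = 15 days.
- *Readmission scored 7.* No rate is given. Each 1% of Part B in hospital on Day 28 for a non-COVID reason after a live discharge would overstate recovery by at most 1 point.

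**5. Mapping to Day 28.** Protocol 6.5 allows ±5 days. SAP 3.8.2 summarizes the ordinal scale by study day without windows, so a status reported on Day 25 or Day 31 has no stated route into the Day 28 row.

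**The case against.** The strongest answer is that for nearly everyone the Day 28 value is a pre-specified endpoint definition, not a gap in the data. Category 7 means only being out of hospital and carries no oxygen grade. Much of that is learned in other ways. Death supersedes discharge. SAP 6.2 takes discharge information from the latest admission after a COVID-19 readmission. The phone contact reviews adverse events, and hospitalization is a seriousness criterion.

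Carry-forward is also partly checked. SAP 6.2.1 plans a second category summary without days missing for reasons other than death or live discharge. The time-to-event analyses censor at the last recorded score. Part B is a single group with no formal testing.

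Most of this stands, and it limits the harm. A reader might infer from the phone restriction that Day 28 status is merely assumed for about half the trial because the question is skipped. The documents do not support that. The SAP rule, not the call, fixes the value, and it does so for live discharges on any day. Phone is an option. The half comes from assumed Day 11 rates. The supplied SAP covers Part B only, so Part A cannot be judged.

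Three things remain. The readmission rule covers only COVID-19 reasons, and no rule feeds serious adverse event data into clinical status. The second summary covers the category table only, not change from baseline, percentage improved or recovered, or oxygen shift, and it leaves the set-to-7 rule untested. The conflict between 6.5 and footnote c is not answered at all.

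**Conclusion.** The point holds in a limited form. The conflict over the phone contact is plain on the face of the documents and must be reconciled. The effect on results is confined to two groups of unstated and probably small size in the descriptive Part B Day 28 summaries: early leavers with a discharge reason other than Discharged Alive who are followed by phone, and participants discharged alive who are in hospital on Day 28 for a non-COVID reason. The Day 11 primary endpoint, its power and Day 28 mortality are unaffected.

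The 10 to 30 participants rest on an assumed 1% to 3%, with everyone in that group exposed, so they bound the first group under that assumption and are not an estimate. If sites follow footnote c, the first group also takes in later leavers with such a discharge reason who are followed by phone. The case for changing the plan is that an observed value costs almost nothing, not that a large bias has been shown.

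**What to change.** - **Protocol 6.5:** delete the parenthesis that limits the phone review of the scale by discharge day. Ask current status at every Day 28 contact: hospitalized or not and, if hospitalized, the level of oxygen support and whether care is ongoing.
- **Protocol Appendix 2 and SAP Appendix 1:** align footnote c, and the sentence that stops other data collection at Day 14 or discharge, with the revised 6.5.
- **SAP 6.2:** state that a reported Day 28 status is used in place of carry-forward and, at least in a sensitivity summary, in place of the set-to-7 rule, with death still superseding. State that a contact within the ±5-day window counts as Day 28.

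Deleting the parenthesis alone would change no analysed value for anyone discharged alive, so the SAP wording has to change with it. The cost is one more question on a contact already planned, edits to three places in the documents, and one extra summary. No visit or participant is added.

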6.6. Clinical Laboratory Assessments

Clinical laboratory assessments are required at screening, Days 1, 3, 5, 8, 10, and 14 or until discharge, whichever comes earlier. Clinical laboratory assessments at other days may be conducted if required by clinical need or local practice. From Day 1 to Day 14, at specified timepoints, the sponsor will be provided with results for the following analytes completed by local laboratories: white blood cell count, hemoglobin and/or hematocrit, platelets, creatinine and creatinine clearance, glucose, total bilirubin, ALT, AST, and any SARS-CoV-2 testing. SARS-CoV-2 testing may include quantitative reverse transcriptase polymerase chain reaction (qRT-PCR) to detect or quantify SARS-CoV-2 or virus sequencing results.

Additional SARS-CoV-2 testing may be conducted at selected sites in a subset of participants. At participating sites, nasopharyngeal swab samples will be collected at Days 1, 3, 5, 8, 10, and 14, sent to a central laboratory, and assayed using qRT-PCR to quantify SARS-CoV-2 viral load. Pretreatment and posttreatment samples with detectable SARS-CoV-2 may be sequenced for resistance monitoring of the viral polymerase gene.

For all clinical laboratory tests at Day 1, at least the most recent result before dosing should be used. For other tests, preferably enter all results if the most recent result before dosing is not possible. When more than 1 result is available in a calendar day, at minimum, results should be reported as indicated in Table 1. All SARS-CoV-2 results should be provided.

Table 1. Data Entry Requirements When Only One Result of Multiple Results Is Recorded for a Given Day

Test Name	Minimum Data to be Recorded
Alanine aminotransferase	Highest result
Aspartate aminotransferase	Highest result
Creatinine	Highest result
Glucose	Lowest result (hypoglycemia) Highest result (hyperglycemia) if outside normal range
Total bilirubin	Highest result
Hematocrit	Lowest result
Hemoglobin	Lowest result
Platelets	Lowest result
White Blood Cells	Lowest result
Creatinine Clearance (Cockcroft-Gault or Schwarz preferred)	Lowest result

6.7. Physical Examination

A targeted physical examination including vital signs (heart rate, respiratory rate, temperature, blood pressure, SpO₂ or PaO₂) should be performed at least daily.

CCI

[REDACTED]

[REDACTED]

6.9. Ordinal Scale

The ordinal scale is an assessment of the clinical status at a given study day. Each day, the worst (ie, lowest ordinal) score from the previous day will be recorded, ie, on Day 3, the lowest ordinal score from Day 2 is obtained and recorded for Day 2. The scale is as follows:

- 1) Death

- 2) Hospitalized, on invasive mechanical ventilation or ECMO
- 3) Hospitalized, on non-invasive ventilation or high flow oxygen devices
- 4) Hospitalized, requiring low flow supplemental oxygen
- 5) Hospitalized, not requiring supplemental oxygen - requiring ongoing medical care (COVID-19 related or otherwise)
- 6) Hospitalized, not requiring supplemental oxygen - no longer requires ongoing medical care (other than per protocol RDV administration)
- 7) Not hospitalized

6.10. Post-treatment Assessments

No assessments are required after Day 28.

6.11. Assessments for Early Discontinuation from Study

If a subject discontinues study dosing (for example, as a result of an AE or clinically significant laboratory abnormality), every attempt should be made to keep the subject in the study and continue to perform the required study-related follow-up and procedures (see Section 3.5, Discontinuation Criteria). If this is not possible or acceptable to the subject or investigator, the subject may be withdrawn from the study.

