3.4. Duration of Treatment

Participants will receive study treatment with RDV for 5 days (treatment group 1), study treatment with RDV for 10 days (treatment group 2), no RDV (treatment group 3), or either 5 or 10 days (Extension Treatment Group). If the participant is discharged, RDV treatment will stop at that time.

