3.5. Discontinuation Criteria

Study drug dosing in an individual subject will be placed on hold and may be discontinued, following a review of all available clinical data by the medical monitor and discussion with the investigator, if any of the following occurs:

- Any SAE or \geq Grade 3 AE suspected to be related to RDV
- Any elevations in ALT $> 5 \times$ ULN; or ALT $> 3 \times$ ULN and total bilirubin $> 2 \times$ ULN, confirmed by immediate repeat testing
- Creatinine Clearance < 30 mL/min

Discontinuation of study medication is not a seriousness criterion.

Subjects who discontinue the study medication should be encouraged to remain in the study and attend study visits as described in Sections 6.3, 6.4, and 6.5.

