6.11.1. Criteria for Discontinuation of Study Treatment

Study medication may be discontinued in the following instances:

- Discharge from the hospital/institution
- Intercurrent illness that would, in the judgment of the investigator, affect assessments of clinical status to a significant degree. Following resolution of intercurrent illness, the subject may resume study dosing at the discretion of the investigator.
- Unacceptable toxicity, or toxicity that, in the judgment of the investigator, compromises the ability to continue study-specific procedures or is considered to not be in the subject's best interest
- Subject request to discontinue for any reason
- Subject noncompliance
- Pregnancy during the study; refer to [Appendix 3](#)
- Discontinuation of the study at the request of Gilead, a regulatory agency or an IRB or IEC

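### Section 6.11 lets an unblinded investigator end a willing participant's follow-up after RDV is stopped, a route that SOC participants do not have and that can cause differential loss at Day 11 and Day 28

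*Protocol*

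**What the plan says.** Protocol section 6.11 opens with the participant who stops dosing: "If a subject discontinues study dosing (for example, as a result of an AE or clinically significant laboratory abnormality", to give its own examples. The first instruction is retention: "every attempt should be made to keep the subject in the study and continue to perform the required study-related follow-up and procedures". The fallback follows: "If this is not possible or acceptable to the subject or investigator, the subject may be withdrawn from the study". No criterion is given for when continued follow-up is unacceptable to the investigator.

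Section 3.5 also aims at retention, in softer terms: "Subjects who discontinue the study medication should be encouraged to remain in the study and attend study visits", with a pointer to the visit schedules in 6.3 to 6.5. It lists the safety events for which dosing is held: RDV-related serious or Grade 3 and higher adverse events, ALT elevation, and low creatinine clearance. Section 6.11.1 adds discharge, toxicity, participant request, noncompliance, pregnancy and this ground: "Intercurrent illness that would, in the judgment of the investigator, affect assessments of clinical status to a significant degree".

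Treatment Group 3 receives no RDV (section 3.4), treatment is not blinded (5.1.2), and participants who leave are not replaced (4.1.1). Section 8.5.1 fixes the Day 11 category for discharge and for death before Day 11. Section 8.3.2 says that missing values are in general not imputed.

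**The concern.** The fallback gives two people a veto over continued follow-up. The participant's veto is a matter of consent. The investigator's is not: as worded, it allows a participant who is willing to stay to be taken out of the study by someone who knows the treatment assignment.

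Because the trigger is stopping study dosing, the route exists in the two RDV arms and has no counterpart on SOC. Toxicity and intercurrent illness can accompany clinical deterioration, and the intercurrent-illness ground is itself defined by its effect on clinical status. If such participants leave before Day 11, the RDV arm may lose poor outcomes that the SOC arm keeps. That would affect the Day 11 comparison, and also Day 28 all-cause mortality if vital status is not sought after withdrawal. No text in 6.11 asks for it.

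The loss is avoidable. Participants are hospital inpatients whose ordinal status is already recorded daily to Day 14 or discharge, so the information would usually sit in the chart.

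**Working it through.** **Step 1. Can the route operate on SOC?** Trigger (6.11): stopping study dosing. SOC (3.4): no RDV. So it cannot. SOC participants may still leave by general withdrawal, since section 8.2.2 foresees premature termination without naming an arm. The asymmetry concerns this route, not all loss.

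**Step 2. Is such a participant's Day 11 score defined?** Discharged before Day 11: category 7. Died before Day 11: category 1, if the death is known. Withdrawn alive and still in hospital: no Part A rule is visible.

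**Step 3. Reproduce the plan's power.** Inputs from section 8.9: SOC Day 11 distribution for categories 1-7 of 0.5, 2.5, 7, 8, 15, 27 and 40%; odds ratio 1.8; two-sided 0.05; 200 per arm.

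- Under odds ratio 1.8 the RDV distribution is 0.28, 1.41, 4.12, 5.06, 10.61, 23.97 and 54.55%.
- Averaging the two arms gives Σp³ = 0.1248, and θ = ln 1.8 = 0.5878.
- Power = Φ(√[N θ² (1 − Σp³)/12] − 1.96) = Φ(√[400 × 0.3455 × 0.8752/12] − 1.96) = Φ(3.175 − 1.96) = 88.8%.

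This agrees with the stated figure of more than 85%, so the same distribution is used below.

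**Step 4. Effect of one-sided loss when RDV does nothing.** Assumption: a share L of one RDV arm is lost, L = 1, 2 or 3% (2, 4 or 6 of 200), and SOC loses nobody by this route. The documents give no rate.

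- Worst pattern considered: all losses from categories 2-4, which hold 2.5 + 7 + 8 = 17.5%. Each of these categories is multiplied by 1 − L/0.175, and the arm is divided by 1 − L.
- Example, L = 2%: factor 1 − 0.02/0.175 = 0.886. The remaining RDV distribution is 0.51, 2.26, 6.33, 7.23, 15.31, 27.55 and 40.82%.
- Fitting a proportional odds model to the expected proportions gives an odds ratio of 1.056.
- Chance of a false finding for RDV in one comparison: 1 − Φ(1.96 − ln OR × √V), with V = n₁n₂n(1 − Σp³)/[3(n + 1)²]. For L = 2%, n₁ = 196, n₂ = 200, n = 396 and V = 29.9, so 1 − Φ(1.96 − 0.300) = 4.8%, against a nominal 2.5% in that direction.

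| Pattern of loss | OR at 1% | OR at 2% | OR at 3% |
|---|---|---|---|
| All from categories 2-4, complete case | 1.027 | 1.056 | 1.087 |
| All from categories 2-5, complete case | 1.022 | 1.046 | 1.070 |
| Half from 2-4, half typical of the arm | 1.014 | 1.028 | 1.042 |
| All from 2-4, carried forward at category 5 | 1.011 | 1.022 | 1.033 |
| Unrelated to outcome | 1.00 | 1.00 | 1.00 |

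In the first row the false-finding probability is about 3.5, 4.8 and 6.6%. These fits omit the baseline-status covariate of the planned model.

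**Step 5. Mortality.** At the assumed 0.5% Day 11 rate, 200 × 0.005 = 1 death is expected per arm. No Day 28 rate is given, so no odds ratio is computed. With counts this low, one unrecorded death would matter.

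**The case against.** The strongest reply is that retention is the operative rule and withdrawal only a fallback. Section 6.11 asks for every attempt first, 3.5 repeats the aim, and 8.5.1 promises an effort to obtain clinical status before discharge in all arms. This is right, and stopping dosing is not in itself a ground for withdrawal. What stands is that the fallback turns on an undefined judgement by an unblinded investigator and overrides a willing participant.

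Four stronger readings are tempting and not supported:

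- *Only RDV participants can be lost.* General withdrawal is open to every arm; only this route is one-sided.
- *The bias must favour RDV.* That needs the lost participants to be worse than average. Stopping for ALT elevation, noncompliance, pregnancy or participant request need not track Day 11 status, and stopping at discharge loses nothing because discharge is scored 7.
- *The treatment-emergent adverse event comparison is biased too.* A participant who stops because of an adverse event already counts: section 8.6.2 counts from randomization, and section 7.5 makes a laboratory abnormality that leads to drug discontinuation an adverse event.
- *The analysis can only carry a better score forward.* Carry-forward appears in the supplied SAP, section 6.2, which covers Part B. That SAP refers to a separate Part A Primary Analysis SAP dated 25 May 2020, which is not supplied, and protocol section 8.3.2 is partly redacted. A Part A rule may exist, and the last recorded score may already be poor. Still, no rule recovers a deterioration that nobody recorded.

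It is also fair to say that the SAP reports the Part A primary analysis as done, and that Part B has one group and so no differential loss. This limits what an amendment can now change; it does not make the protocol wording sound for the randomized comparison.

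**Conclusion.** The point holds as a weakness in the protocol text that should be corrected. Section 6.11 permits loss that is linked to stopping RDV, decided without blinding, and possibly related to outcome, in the Day 11 comparison and in Day 28 mortality.

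The effect is probably modest. At 1-3% loss, all from categories 2-4, the null odds ratio moves to 1.03-1.09, small beside the target of 1.8, although 4 of 200 lost in that pattern roughly doubles the chance of a false finding for RDV in one comparison. The figures rest on an assumed rate, an adverse pattern of loss and, except in the carry-forward row, complete-case analysis. Nothing supplied shows that such withdrawals occurred. Confidence is medium, because the Part A SAP might narrow the gap.

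**What to change.** In protocol section 6.11:

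1. Delete 'or investigator', and state that stopping study drug is not a ground for ending follow-up.
2. Add that, unless consent to data collection is withdrawn, ordinal status through Day 14, discharge date and status, and vital status at Day 28 continue to be taken from the hospital record in all arms, including when study visits are not possible. This second sentence is needed because deleting two words would leave impossibility of follow-up as a ground for withdrawal.

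The criteria for stopping study drug are not changed. The cost is two sentences in an amendment and a few more chart entries, with no new visits or procedures. Part A data already analysed cannot be changed by new wording; there, reporting withdrawals by arm and reason would show whether the route was used.
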